**Outcome C: Creatinine re-testing**

Attribute	Description
Population	Adults who receive a creatinine test result at a primary healthcare center suggesting low eGFR (<60 ml/min/1.73 m  ) and thus are indicated for a re-test within six months
Treatment	Intervention: New clinical decision support triggering system designed to manage chronic kidney disease, implemented at healthcare centers using the ALMA platform Control: Standard ALMA CDS platform
Endpoint	Undergoing a creatinine re-test within six months of a test result which indicated a re-test
Summary measure	1. Ratio of proportions (risk ratio) 2. Absolute difference of proportions (risk difference)
Intercurrent events	As above

**Outcome D: Albuminuria re-testing**

Attribute	Description
Population	Adults who receive an abnormal albuminuria test result at a primary healthcare center of dipstick test denoting KDIGO A2+ or a urinary albumin to creatinine (uACR) test >3 mg/mmol and are thus indicated for a re-test within six months
Treatment	Intervention: New clinical decision support triggering system designed to manage chronic kidney disease, implemented at healthcare centers using the ALMA platform Control: Standard ALMA CDS platform
Endpoint	Undergoing an albuminuria re-test within six months of a test result which indicated a re-test
Summary measure	1. Ratio of proportions (risk ratio) 2. Absolute difference of proportions (risk difference)
Intercurrent events	As above

#### 4.4 Analysis populations

The unit of observation is the individual patient. Each patient will only be included once in each analysis.

For outcomes A and B, each patient will be included at the time of their first visit during the recruitment phase: we will refer to this as their Index date for that outcome. This will be used as the start time for the 12 months window for testing.

For outcomes C and D, each patient will be included at the time of their results from their creatinine (C) or albuminuria (D) test: we will refer to this as their Index date for that outcome. This will be used as the start time for the 6 months window for re-testing.

There will be an analysis population associated with each of the four outcomes listed above (A-D). Randomisation occurred in September 2023; however, we will allow a four-month run-in period for the new system. Recruitment of individual participants will begin on 1st January 2024. For outcomes A and B, recruitment will close on 31st December 2024, to allow 12 months of follow-up for all patients. For outcomes C and D, recruitment will close on 30th June 2025, to allow six months of follow-up for all patients.

**Modified ITT population A:** All patients who attend a visit at one of the study health centers during 2024 and who remain alive and registered at that center for a further 12 months, and are eligible for annual kidney function screening.

**Modified ITT population B:** Same as Modified ITT population A (above)

**Modified ITT population C:** All patients who receive a test result for creatinine from one of the study health centers between 1st January 2024 and 30th June 2025, who remain alive and registered at that center for a further six months, and have an indication for a re-test.

**Modified ITT population D:** All patients who receive a test result for albuminuria from one of the study health centers between 1st January 2024 and 30th June 2025, who remain alive and registered at that center for a further six months, and have an indication for a re-test.

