## 2 Objectives

The objective of the ALMA study is to evaluate the effectiveness of the CDS trigger to ensure that people who meet the criteria for CKD testing are invited to test and are actually tested.

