## 2.2 Other secondary outcomes

There are four non-test related secondary outcomes:

**Outcome 2.1 CKD diagnosis:** Proportion of patients meeting indication who receive a diagnosis of CKD (according to ICD-10) within six months of eGFR / A2 re-testing. By “indication” we mean eGFR<60 ml/min/1.73 m^2 and/or dipstick A2+ or >3 mg/mmol at re-test. Only patients with at least six months of follow-up after their re-test and who are CKD-negative at the first visit will be included in this analysis (that is, re-test must occur on or before 30 June 2025).

**Outcome 2.2 Initiation of new CKD-treatment:** The proportion of patients who start new CKD-modifying treatment within six months of re-test indicating a CKD diagnosis (as defined above).

**Outcome 2.3 Referral for ultrasound:** The proportion of patients meeting the criteria for nephrologist care who receive a referral for ultrasound of the kidneys.

**Outcome 2.4 Accepted to nephrologist care:** The proportion of patients meeting the criteria for nephrologist care (according to Swedish guidelines) who are newly accepted into care. By “newly accepted” we mean we will exclude patients who have had a visit with a nephrologist in the two years prior to their first visit to a participating healthcare center during the trial period.

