### **3.4 Sample size**

The study was adequately powered to detect an absolute improvement in our primary study outcome of 13% with an alpha of 5%. To calculate the power of our trial, we evaluated the processes of care in the 66 primary healthcare centers during 2019 as collected in the SCREAM project. We chose this year prior to the COVID-19 pandemic to have more objective estimations of health use not affected by and policies during the pandemic. During 2019, 662 995 unique individuals visited those primary healthcare centers at least once. Of those, 92 011 were eligible for screening/testing of kidney function: 66% took a creatinine test, and 34% took a creatinine test. Of people with first detected eGFR<60 ml/min/1.73 m^2 or albuminuria, 59% and 28% were retested for creatinine or albuminuria within 3-6 months.

We assumed a recruitment period of 12 months and a total of 33 health center (clusters) per arm with the same number of patients as in 2019. We estimated the intraclass correlation for the outcomes to be 0.1 (as quantified in the UK trial by Major et al, J Am Soc Nephrol. 2019 Jul;30(7):1261-1270.). The table below gives the originally calculated power, and the power we now have, conservatively assuming 32 clusters per arm.

Comparison	Original power (33 clusters per arm)	New power (32 clusters per arm)
A. Primary outcome: Detect an increase of people having a creatinine test from 66% to 79%	86%	85%
B. Detect an increase of people having a albuminuria test from 34% to 48%	84%	83%
C. Detect an increase of people having a re-test of creatinine from 59% to 73%	86%	82%
D. Detect an increase of people having a re-test of albuminuria from 28% to 42%	86%	84%

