## 6 ANALYSIS

### 6.1 Analysis methods

The same analysis methods will be used for all outcomes defined above. In all analyses we will always adjust for the randomization factor of cluster size (either “large” or “not-large”) and the cluster-level proportion with that outcome in the 12 months preceding the start of the trial. For the two centers which merged we will combine the data and treat as one entity. The precise means of adjustment will depend on the analysis method, see below for details.

We will perform both an individual-level analysis (to estimate risk ratios) and a cluster-level analysis (to estimate risk difference).

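### Entry to outcomes C, D, 2.1 and 2.2 depends on testing done after randomisation, which the intervention is meant to raise, and the SAP does not allow for this

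*SAP*

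**What the plan says.** - **Entry to C and D (section 4.4).** Population C is "All patients who receive a test result for creatinine from one of the study health centers between" 1 January 2024 and 30 June 2025, and population D is "All patients who receive a test result for albuminuria from one of the study health centers between" the same dates. Both also require a re-test indication and six further months alive and registered. The Index date is the result. Randomisation took place in September 2023.
- **Estimands (section 4.3.2).** The Population rows read "Adults who receive a creatinine test result at a primary healthcare center suggesting low eGFR" and "Adults who receive an abnormal albuminuria test result at a primary healthcare center of dipstick test denoting KDIGO A2" and so on. The intercurrent events, carried over from the primary estimand, are death and transfer only.
- **Outcomes 2.1 and 2.2 (section 2.2).** Outcome 2.1 counts CKD diagnoses after an abnormal re-test. Outcome 2.2 is "The proportion of patients who start new CKD-modifying treatment within six months of re-test indicating a CKD diagnosis".
- **Purpose of the trigger.** Section 2 wants to ensure that "people who meet the criteria for CKD testing are invited to test and are actually tested". Section 3.4 plans for creatinine testing to rise from 66% to 79%, albuminuria testing from 34% to 48%, and re-testing from 59% to 73% (C) and 28% to 42% (D).
- **Analysis.** Section 6.1 applies the same methods to every outcome. Section 6.1.1 adds covariates only when the arms differ by more than 20% (binary) or by a factor above 1.2 (means). The time-to-event analysis in 6.3 runs from the Index date. The one sensitivity analysis (6.5) drops a single centre.
- **Reporting.** N is shown by arm (Shell Table 2a) and by centre (Shell Table 3). Section 5.4 promises baseline characteristics for each population, but the only baseline shell (Shell Table 1) covers screening-eligible patients.

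**The concern.** A patient reaches C or D only by being tested and found abnormal after the centre was randomised. Outcomes 2.1 and 2.2 add a second such step, the re-test. The intervention targets both steps. If it works on A and B, the intervention-arm denominators for C, D, 2.1 and 2.2 contain patients whose counterparts in the standard arm were never tested.

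The Population rows state the conditioning but not that the arm can alter it. Centres remain compared as randomised, while the patients inside these subsets need not be alike. A between-arm difference can then mix an effect on re-testing, diagnosis or treatment with a change in who was tested. C and D are two of the four key outcomes, each with its own estimand, power figure, effect size and p-value, so a reader would naturally take the contrast as an effect on re-testing.

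No claim is made for outcomes 2.3 and 2.4, whose entry criteria are not written out.

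**Working it through.** The point is structural, so there is no stated figure to reproduce. The arithmetic shows what size the effect could take.

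**Inputs from section 3.4.** Testing rate t0 to t1: 0.66 to 0.79 (creatinine), 0.34 to 0.48 (albuminuria). Usual re-test rate r0: 0.59 (C), 0.28 (D).

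**Assumptions not in the SAP.** The 12-month testing rates are applied to the 18-month entry window. The system has no effect on re-testing. Three quantities are varied:
- f = share of standard-arm entrants who are screening-eligible (section 4.4 does not limit C and D to them)
- a = abnormality of newly tested patients relative to the rest
- q = their re-test rate relative to the rest, 0.5 to 1.5

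**Formulas.** Newly tested entrants per standard-arm entrant: n = f × a × (t1 − t0)/t0. Their share of intervention-arm entrants: s = n/(1 + n). Apparent re-test rate: r0 × (1 − s + q × s).

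**Case f = 1, a = 1.**
- C: n = 0.13/0.66 = 0.197 and s = 0.165. The apparent rate runs from 54.1% (q = 0.5) to 63.9% (q = 1.5), against 59%.
- D: n = 0.14/0.34 = 0.412 and s = 0.292. The apparent rate runs from 23.9% to 32.1%, against 28%.

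**Largest spurious difference, in percentage points, for q = 0.5 or 1.5:**

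| f | a | s (C) | C | s (D) | D |
|---|---|---|---|---|---|
| 1 | 1.5 | 0.228 | ±6.7 | 0.382 | ±5.3 |
| 1 | 1 | 0.165 | ±4.9 | 0.292 | ±4.1 |
| 1 | 0.5 | 0.090 | ±2.6 | 0.171 | ±2.4 |
| 0.5 | 1 | 0.090 | ±2.6 | 0.171 | ±2.4 |
| 0.5 | 0.5 | 0.047 | ±1.4 | 0.093 | ±1.3 |

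At q = 1 every entry is zero. The planned difference is 14 points for both outcomes.

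**Against precision.** The section 3.4 power with 32 clusters per arm implies SE = 0.14/(1.96 + z(power)). For C (82%) this is 0.14/2.875 = 0.049, and for D (84%) it is 0.14/2.954 = 0.047. The f = 1, a = 1 extremes are therefore about 1.0 SE (C) and 0.9 SE (D), and the ±2.6 and ±2.4 cases about half an SE. A 3-point shift would raise the two-sided false-positive risk from 5% to about 9–10%.

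**Would the covariate rule in 6.1.1 catch it?** Read as percentage points, the shift in a binary covariate is s times the prevalence gap between newly tested patients and the rest, so it cannot exceed s.
- C, f = 1: the maximum is 16.5 points at a = 1, below 20. It can pass 20 only if a exceeds 0.25 × 0.66/0.13 = 1.27.
- D, f = 1, a = 1: a prevalence gap above 20/0.292 = 68.6 points is needed.
- Means, f = 1, a = 1: with k the ratio of means, 1 + s(k − 1) > 1.2 requires k above 2.22 (C) or 1.69 (D). In the other direction D needs k below 0.43, and C cannot reach the threshold for a positive variable.

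Read as a relative 20%, the binary rule could fire more easily. On either reading it covers measured variables only.

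**Other planned analyses.** Time to event starts at the result, after selection has happened. Dropping one centre and the subgroup analyses by visits and sex do not bear on entry.

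**The case against.** The strongest reply is that nothing is misstated. Re-testing among patients with an abnormal result is a coherent clinical question, and the SAP defines it openly and consistently. That stands, and is why the definitions should stay. What is missing is recognition that the contrast is not protected by randomisation at patient level.

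The sizes are also conjectural. The 13- and 14-point testing gains are planning differences, not forecasts, and a smaller gain shrinks every figure. In 2019 only 92 011 of 662 995 visitors were screening-eligible, and f among abnormal results is unknown and could be below 0.5. Several cases in the table are half an SE or less. This stands too: the figures show a possible scale, not an expected bias.

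Much of the reporting is already planned, in section 5.4 and Shell Tables 2a and 3. It would reveal a difference in entry, but the SAP does not say how to read the results if one appears.

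Finally, a comparison over population A answers a different question from C or D. This is true, and it must be labelled so. It does supply a contrast that is not selected by testing.

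A minor point: a CKD diagnosis made during the run-in could itself confer eligibility for A and B, so these are not wholly sealed off. That route is marginal and does not change the point about C, D, 2.1 and 2.2.

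**Conclusion.** The concern holds. Entry to C, D, 2.1 and 2.2 follows randomisation and runs through testing that the intervention is designed to increase. Nothing in the estimands, methods or sensitivity analysis deals with it.

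The direction cannot be known from the SAP. Under the assumptions listed, the spurious difference for C and D runs from zero to ±6.7 and ±5.3 points respectively, and it is ±4.9 and ±4.1 with equal abnormality and all entrants screening-eligible. No size is given for 2.1 and 2.2. The conditional proportions remain legitimate measures of care, but a difference in them cannot be read alone as an effect on re-testing, diagnosis or treatment. The primary outcome does not condition on a test result. This is a worthwhile and cheap improvement to the secondary analyses, not a threat to the main conclusion.

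**What to change.** Keep C, D, 2.1 and 2.2 as defined, and make these changes:

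1. In the estimands for C and D and the definitions of 2.1 and 2.2, add a sentence saying that the intervention may change who enters, so the contrast is conditional and not protected by randomisation at patient level.
2. Beside each result, report by arm the numbers tested, the numbers abnormal and the case-mix of entrants, with a baseline shell for each population.
3. Add one supplementary comparison each for C and D with all modified ITT population A patients as denominator. The event is an abnormal first result within six months of the index visit plus a re-test within six months of that result. Describe it as the effect on the whole pathway. With unchanged re-testing and equal abnormality it would still give risk ratios of 79/66 = 1.20 (C) and 48/34 = 1.41 (D).
4. Analogous comparisons for 2.1 and 2.2 are optional.

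**Cost.** One sentence per outcome, a small table and two analyses on data already held. The timing fits section 3.7: 31 December 2024 plus six plus six months is 31 December 2025. Section 6.1 adjusts for "the cluster-level proportion with that outcome in the 12 months preceding the start of the trial", so each composite needs a prior proportion. Its pathway lasts up to 12 months after the visit, so a full visit year needs up to 24 months of earlier data. Under the 2019 adjustment in 6.1.1 and 6.1.2 it would run into 2020. The simple alternative is to use the prior proportion for A or B and say so. Absolute differences will be smaller, and only screening-eligible patients with a 2024 visit are covered.

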## 5 TRIAL POPULATION

### 5.1 Screening data

Individual patients are not screened for entry other than requirement to be eligible for screening / re-test defined above. All consenting Primary Healthcare Centers in Region Stockholm are included in the trial.

### 5.2 Eligibility

There are no eligibility checks for individual patients.

### 5.3 Withdrawal / Follow-up

It is not anticipated that any center will withdraw from the study; if it happens we will decide what to do on a pragmatic, case-by-case basis. Using the SCREAM database we will be able to access relevant patient data for all patients in the 12 months of the study recruitment, up to 12 months after the final patient has been registered.

### 5.4 Baseline patient characteristics

We will report baseline patient characteristics for each analysis population, both at an individual level (summarized by arm) and summarized for each cluster.

## 6 ANALYSIS

### 6.1 Analysis methods

The same analysis methods will be used for all outcomes defined above. In all analyses we will always adjust for the randomization factor of cluster size (either “large” or “not-large”) and the cluster-level proportion with that outcome in the 12 months preceding the start of the trial. For the two centers which merged we will combine the data and treat as one entity. The precise means of adjustment will depend on the analysis method, see below for details.

We will perform both an individual-level analysis (to estimate risk ratios) and a cluster-level analysis (to estimate risk difference).

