### 3.2 Randomization

Randomization was restricted to ensure (approximate) balance on two factors, based on 2019 (pre-Covid) levels:

- Number of people eligible to be tested for albuminuria
- Proportion of people actually tested for albuminuria

We restricted the randomization as follows:

- There were four centers with an eligible population much larger than the other 62 centers

- Husläkarmottagning Handen = 5434
  - Ektorp = 4712
  - Liljeholmens vårdcentral = 3762
  - Jakobsberg vårdcentral = 3286
  - No other center had a 2019 eligible population greater than 3000
- We first created 10,000 randomizations of the 62 “non-large” centers, such that 31 were in each arm.
- We then created all possible permutations of the four large centers such that two were in one arm and two were in the other arm. There are six possible permutations which achieve this (AABB, ABAB, ABBA, BAAB, BABA, BBAA)
- We combined these two sets to give us 60,000 potential randomizations
- We then mirrored these allocations to give us 120,000 randomizations (that is, reversed the allocation of intervention and standard arms)
- For each potential allocation we calculated the average proportion of people tested in 2019. (This was calculated on a center level, not a population level, so the denominator was 33 in each arm.)
- If the difference in the average proportion between the arms was greater than 3.7% we discarded the allocation. The figure of 3.7% was chosen because, under different randomly drawn sets of the initial 10,000 allocations, 3.7% ensured that around, but less than, 10% of the final 120,000 allocations were discarded. And further, it was felt that 3.7% was small enough such that if there was indeed a between-arm difference of 3.7% we would still be confident that the two arms were similar enough to be confident of drawing unbiased conclusions from the results.
- Finally, one allocation was randomly selected from the remaining allocations

The code to perform this randomization was written by the trial statistician (SN) and then given to an independent statistician, outside of the study team, who changed the random seed which selected the 10,000 allocations, and the random seed which selected the final allocation. When the code was run, 10,348 (8.6%) allocations were removed due to a difference between the arms in 2019 test rates, and hence the final allocation was chosen from 109,652 possible allocations.

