### **3.3 Post-randomization change**

Four days after randomization the study team were informed that two of the 66 centers had been merged into one administrative unit (although still on separate sites). These two centers were Bredäng and Sätra; their new name is “Bredäng Sätra vårdcentral”. Due to the merger we will not be able to retrieve outcome data at a lower level than the merged center. As by chance these two centers had been assigned to the same arm (the intervention) we decided to proceed with the trial under the original randomization. We note here that the two original restrictions still held after the merger of these centers:

1. the population of the new center is 1,455, which means it ranks 24th (of 65) in size
2. the difference between the two arms in terms of 2019 test rates is now 3.4% (< 3.7%)

This SAP is written to reflect that change. We will analyze the study with 65 centers (33 in the standard arm and 32 in the intervention).

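### The SAP does not settle whether the primary analysis adjusts for the 2019 albuminuria-testing proportion on which randomization was restricted, and no reading combines it with the outcome's own baseline

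*SAP*

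**What the plan says.** SAP 3.2 names two restriction factors, both at 2019 levels: "Number of people eligible to be tested for albuminuria" and "Proportion of people actually tested for albuminuria". The second was enforced by a limit on the difference between arm means of the center proportions: "If the difference in the average proportion between the arms was greater than 3.7% we discarded the allocation". SAP 3.3 reports that after two centers merged this difference is 3.4 points. It does not say which arm is higher.

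The covariates are defined in three places.

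- SAP 6.1, for all outcomes: "In all analyses we will always adjust for the randomization factor of cluster size", and also "the cluster-level proportion with that outcome in the 12 months preceding the start of the trial".
- SAP 6.1.1, individual-level model (risk ratio): center size and the 2019 outcome proportion, entered linearly, with a remark in brackets that this proportion was used in the randomization.
- SAP 6.1.2, cluster-level analysis (risk difference): center size and the 2019 outcome proportion, without that remark.

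Further covariates enter only under the large-imbalance rule in 6.1.1: an arm difference above 20% for a binary variable, or a ratio of arm means above 1.2 for a continuous one.

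**The concern.** A trial restricts its allocation on a factor because it expects that factor to predict outcome, and the usual consequence is to adjust for it. Here one of the two factors, size, is carried into every analysis by name. The other is replaced by "the cluster-level proportion with that outcome", which changes with the outcome and is an albuminuria-testing proportion only for B. The primary outcome is creatinine testing.

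The arms are known to differ on the factor. If a center's albuminuria-testing habit in 2019 predicts later creatinine testing beyond the center's own creatinine baseline, the primary contrast moves in the direction of that difference. The three covariate definitions also disagree, so two analysts could fit different primary models and both claim to follow the plan. The SAP was approved on 20 November 2025 and outcome measurement closes on 31 December 2025, so the choice should be fixed in writing before the outcomes are analyzed.

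**Working it through.** **1. The covariate set for outcome A under each reading**

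| Reading | Individual-level model | Cluster-level model |
|---|---|---|
| By outcome (6.1, 6.1.2, and 6.1.1 without its remark) | size + creatinine testing | size + creatinine testing |
| By the 6.1.1 remark | size + 2019 albuminuria testing | size + creatinine testing |

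Neither row has a model with both the restriction factor and the outcome's own baseline. For C, D and 2.1-2.4 the own-outcome proportion is again not albuminuria testing. For B the two coincide only if the period is 2019 (6.1.1, 6.1.2). Under 6.1 the period is the 12 months before the trial, so even B would not contain the exact factor.

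**2. Does the large-imbalance rule bring the factor in?**
The difference of 3.4 points is below 20. For the ratio, take a mean near 34%. This is an assumption: it is the 2019 rate that row B of the power table in SAP 3.4 uses for albuminuria testing. The arm means are then about 35.7 and 32.3, and 35.7/32.3 = 1.11, below 1.2. A 3.4-point gap would reach 1.2 only if the lower mean were at most 3.4/0.2 = 17%. The rule pools patients and the 3.4 is a mean over centers, so the pooled figure may differ, but it would have to be far larger to trigger the rule.

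**3. How unusual is 3.4 points?**
SAP 3.2 reports "10,348 (8.6%) allocations were removed due to a difference between the arms in 2019 test rates". Check: 10,348/120,000 = 8.62% and 120,000 - 10,348 = 109,652, both as stated. The 3.4 itself needs center-level data and cannot be recomputed.

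Normal approximation: a two-sided tail of 0.0862 gives z = 1.716.
- SD of the arm difference = 3.7/1.716 = 2.16 points.
- Implied between-center SD = 2.16/sqrt(2/33) = 8.8 points.
- 3.4/2.16 = 1.58 SD, two-sided tail 0.115.
- Share of retained allocations further apart = (0.115 - 0.086)/(1 - 0.086) = about 3%.

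The SD refers to 66 centers and the 3.4 to 65, so these are approximate.

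**4. What could remain in the estimate for A?**
Let r be the correlation between a center's baseline creatinine and albuminuria testing. Let b be the points of later creatinine testing predicted per point of 2019 albuminuria testing, given own baseline. The SAP gives neither. In a linear center-level model adjusted for own baseline only, the expected residual is

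residual = 3.4 x b x (1 - r²).

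| r | b | Formula (points) | Simulated residual | SE, own baseline only | SE, both |
|---|---|---|---|---|---|
| 0.3 | 0 | 0 | 0.01 | 1.58 | 1.61 |
| 0.3 | 0.1 | 0.31 | 0.32 | 1.70 | 1.73 |
| 0.3 | 0.2 | 0.62 | 0.65 | 1.77 | 1.81 |
| 0.6 | 0.2 | 0.44 | 0.41 | 1.68 | 1.69 |
| 0.8 | 0.2 | 0.24 | 0.24 | 1.65 | 1.66 |

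The simulations had 65 centers, the imbalance fixed at 3.4 points, no true effect, and creatinine testing given the same 8.8-point center spread. With both covariates the residual was about 0 and the SE rose by up to about 2%.

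A separate simulation with partial correlations of 0.2 to 0.3 gave a residual of 0.25 to 0.44 of an SE. At adjusted SEs of 1.6 to 1.8 points that is 0.25 x 1.6 = 0.4 to 0.44 x 1.8 = 0.8 points.

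The size in points scales with the center spread. The SAP's ICC of 0.1 at 66% implies sqrt(0.1 x 0.66 x 0.34) = 15.0 points. At the same standardized relations, residual and SE would both be 15.0/8.8 = 1.7 times as large, and their ratio would not change.

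**The case against.** The strongest reply is that 6.1.1 does tie its covariate to the randomization, and the proportion used there was albuminuria testing. On that reading the individual-level model for A already contains the factor. This stands in part. A reader of 6.1 alone might infer a settled omission, and the text does not support that; it is contradictory. The remark does not repair the plan, however. Under it A loses the own baseline that 6.1 says is always adjusted for, and the cluster-level analysis still lacks the factor.

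Second, adjusting A for its own baseline, normally the stronger predictor, absorbs whatever the two testing habits share. This stands, and it is why the residual is a fraction of 3.4 points.

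Third, 3.4 points lies inside a limit that the SAP set in advance and justified. Allocations were mirrored, so the procedure favors neither arm, and about 11% of unrestricted allocations would be further apart. This also stands: it is chance imbalance in one allocation, not a bias of the design. But meeting the limit makes an allocation acceptable; it does not make adjustment for the factor superfluous.

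**Conclusion.** The point holds as a contradictory covariate definition that can leave a known imbalance unadjusted in the primary analysis. The covariate sets in step 1 and the failure of the large-imbalance rule follow from the SAP's text and figures, the 1.11 ratio resting on a mean near 34%.

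A reader might go further and infer that the primary estimate is biased by the 3.4 points, or that power is materially changed. The documents do not support either. The residual depends on a correlation the SAP does not report. Under the assumptions tried, with a center spread of 8.8 points, it is 0 to about 0.8 points on a 13-point target. It would be proportionately larger if the spread were wider, and its direction is unknown because 3.3 does not give one. No residual was calculated for C, D or 2.1-2.4; for these only the omission is shown.

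This is a worthwhile, inexpensive correction and does not call the trial's validity into question.

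**What to change.** - In 6.1, 6.1.1 and 6.1.2, state in identical words that every analysis adjusts for both randomization factors: center size (large or not large) and the center's 2019 albuminuria-testing proportion (linear, merged center as one unit). Add to these the outcome's own baseline proportion from one stated period.
- Say that for outcome B the two proportions are the same variable if the stated period is 2019.
- Correct the remark in 6.1.1, so that only the albuminuria-testing proportion is described as used in the randomization.
- In 3.3, state which arm has the higher 2019 proportion.

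The cost is SAP wording only, because the variable was compiled for every center at randomization. The statistical cost is one center-level degree of freedom and an SE about 1-2% larger if the factor is not predictive.
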